18.0 Provisions to Monitor the Data to Ensure the Safety of Subjects

18.1 Describe:

- The plan to periodically evaluate the data collected regarding both harms and benefits to determine whether subjects remain safe will occur throughout each experimental visit.

- Any unanticipated adverse events reported will be recorded.
- The safety information will be collected at every study visits.
- The frequency of data collection, including when safety data collection will occur at every study visit.
- The PI and the research team will review the data. If further review is necessary, the research team will recruit the associate dean of research for the College of Education, Health, and Human Sciences.
- N/A
- N/A
- N/A

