3.0 Background

Though not fully understood, sleep is accepted to be a paramount mediator of homeostasis (1). Indeed, sleep allows the human body to both recover from as well as restore the metabolic, hormonal, neural, immunological, cognitive, and even emotional processes that it carries out during the waking hours of the day (2–6). This ultimately serves to prime the body for functional optimization the following day, assuming enough sleep is achieved (6–8). Echoing sleep's importance, though from the opposite perspective, is the effect that inadequate sleep has on the body. Disordered or disturbed sleep (i.e., sleep habits/conditions resulting in insufficient sleep quantity and/or quality), for example, has been shown to be associated with impaired cognitive function, hypertension, increased arterial stiffness (i.e., impaired vascular function), increased sympathetic activity, reduced fine-motor skills, as well as undesirable mood states (9–13). In conjunction, many of these symptoms have been shown to increase an individual's risk for cardiovascular disease (CVD) (14). This ominous relationship between poor sleep and CVD risk is particularly noteworthy given that approximately one-third of the American population do not achieve the amount of sleep recommended by the American Academy of Sleep Medicine (15,16). Moreover, this chronic sleep insufficiency represents a state of partial sleep deprivation (PSD) (5) and poses a legitimate threat of cardiovascular events (17–19). This is particularly noteworthy, as acute bouts of PSD, defined as two or more consecutive nights of insufficient sleep (20), are common in young adults, especially college students (21,22), putting them at an increased risk of an event.

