4.0 Study Endpoints

- 4.1 The primary and secondary study endpoints are as follows:
 - Do individuals with higher CRF exhibit differing central hemodynamic responses to acute partial sleep deprivation compared to individuals with lower CRF.
 - Do individuals with higher CRF exhibit differing central cardio-autonomic function responses to acute partial sleep deprivation compared to individuals with lower CRF.
 - Do individuals with higher CRF exhibit differing central serum cytokine responses to acute partial sleep deprivation compared to individuals with lower CRF.
 - Do individuals with higher CRF exhibit differing central psychological mood state responses to acute partial sleep deprivation compared to individuals with lower CRF.

- Do individuals with higher CRF exhibit differing central RSI responses to acute partial sleep deprivation compared to individuals with lower CRF.
- Do individuals with higher CRF exhibit differing central PVT responses to acute partial sleep deprivation compared to individuals with lower CRF.

4.2 *Describe any primary or secondary safety endpoints.*

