
6.2 Research Procedures

Initial Visit: All data collection time points are outlined in Figure 1 below. Prior to participation, voluntary consent to participate will be obtained. Eligible participants (i.e., those deemed fit to participate via the Physical Activity Readiness Questionnaire [PAR-Q+] in conjunction with the American College of Sports Medicine guidelines for physical activity) will then complete a questionnaire to establish typical training characteristics (i.e., frequency, intensity, time, type, and history). Specifically, the PAR-Q+ screens individuals for signs or symptoms of cardiovascular, metabolic, and or renal disease which would make it inadvisable for them to participate in physical activity. Individuals who are not deemed fit to participate, according to the PAR-Q+, will not be allowed to continue with participation. They will then be assessed for body composition (Bod Pod; Cosmed, Chicago, IL) prior to performing a maximal treadmill test (protocol described below) to determine maximal oxygen consumption capacity (VO_{2max}). In the case that an individual does not qualify for the study (i.e., those meeting requirements for training status and VO_{2max}), all data collected on that individual will be destroyed. Individuals who do qualify will be provided with a WHOOP (Boston, MA) wearable, wrist-worn multi-sensory biometric and cardio-autonomic function monitor. The WHOOP band will be worn on the non-dominant wrist throughout the entirety of the project timeline (~1.5 months), including a two-week initialization period prior to the first data collection visit. Participants will then be familiarized with daily sleep, physical activity, and 3-day nutrition logs as well as a PVT smart phone application, all of which will be performed throughout the study. Specifically, participants will complete the sleep and physical activity logs and PVT task daily throughout the enrollment period, while they will complete the 3-day nutrition log in the 3 days immediately prior to Post Test 1 and 2 visits (described in detail below). Lastly, participants will be assessed for sleep chronotype via a morningness-eveningness questionnaire to inform any potential differences in sleep intervention response post hoc.

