15.0 Risks to Subjects

- 15.1* The reasonably foreseeable risks, discomforts, hazards, or inconveniences to the subjects related the subjects' participation in the research include:
- Physical discomfort from intravenous blood draws: Yet, blood will be taken by researchers previously trained and experienced in phlebotomy, following the biological safety procedures in place for a level two laboratory.
 - Possible inconvenience of missing work if they adhere to a traditional work schedule: Yet we can schedule experimental visits early in the morning before traditional hours to accommodate these needs.
 - Possible risk of adverse cardiac event or injury during maximal treadmill testing: Yet, the established risk of event is 6 in 10,000 and the tests will be performed by researchers previously trained and extensively experienced (10+ years) in administering the test.
- 15.2* Unforeseeable risks may include the expression of a genetic condition that was not "caught" by the screening process. Yet, efforts will be made to ask the subject if there is any reason why they think it is to their detriment if they participate in this protocol.
- 15.3* N/A. Pregnant women will not be included in this study
- 15.4* Blood will be collected following biological safety procedures in place for a level 2 laboratory. However, accidental needle sticks or exposure to potential pathogens via blood is always a possibility. In such a case, wounds will be cleaned and bandaged appropriately and incidents will be reported.

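### The only explicit adverse-event rule covers unanticipated, reported events, so anticipated events under sleep restriction or treadmill testing may go unrecorded and could not be reliably compared between conditions

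*Combined protocol and SAP*

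**What the plan says.** Section 18.1 states which adverse events are kept in a single sentence: "Any unanticipated adverse events reported will be recorded". The same list adds two general commitments. One is "The plan to periodically evaluate the data collected regarding both harms and benefits to determine whether subjects remain safe", placed within each experimental visit. The other is "The safety information will be collected at every study visits". Neither says what is asked, how an event is defined or graded, or how it is tied to a sleep condition.

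Section 15.1 introduces "The reasonably foreseeable risks, discomforts, hazards, or inconveniences to the subjects" and lists three: "Physical discomfort from intravenous blood draws", missed work, and a cardiac event or injury during the maximal treadmill test, put at 6 in 10,000. Section 15.2 adds a genetic condition missed at screening. Section 15.4 adds needle sticks and exposure to pathogens, with incidents to be reported.

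Section 3 associates disturbed sleep with impaired cognition, hypertension, reduced fine-motor skills and poor mood. It says that chronic insufficiency "poses a legitimate threat of cardiovascular events", and the next sentence carries the concern over to acute partial deprivation in young adults.

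Section 4.2 still holds only its template prompt, "Describe any primary or secondary safety endpoints". Section 6.2 says that, for anyone who does not meet the training-status and VO2max requirements, "all data collected on that individual will be destroyed".

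**The concern.** Sleep restriction is the trial's only active intervention (Section 1.0), yet the risk section does not mention it and the recording rule filters events twice: they must be unanticipated, and they must be reported. Under that rule the safety record could lack the kinds of event that a reader would most want to see by condition.

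The exposure happens at home. Post-Test visits come after each 4-day period (Sections 6.1 and 6.2), so no laboratory visit falls within the restriction, and an incident there reaches the record only if the participant mentions it. Participants know which bed times they were given, so unprompted reporting could also differ between conditions.

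The destruction rule operates after the maximal treadmill test, the one procedure for which the protocol puts a number on the risk. An event in someone who then fails the fitness limits could be erased with the rest of that person's data.

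**Working it through.** This is mainly a comparison of texts. The plan states no event count or safety figure to reproduce, apart from the 6 in 10,000 used in step 4.

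**1. Risks named against the intervention.** Sections 15.1, 15.2 and 15.4 name 3 + 1 + 1 = 5 items. None concerns sleep restriction. Safety endpoints defined in 4.2: none. Sentences stating which adverse events are recorded: one, limited to unanticipated events.

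**2. Two readings of the undefined term.**
- *Unanticipated means not listed in Section 15.* A sleepiness-related incident at home is then recordable if reported. Treadmill injury and blood-draw discomfort are listed, so the rule does not commit to recording them.
- *Unanticipated means not expected from the protocol's own background.* Sleep-related lapses, clumsiness and low mood are then anticipated from Section 3, and the rule does not commit to recording them.

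Each reading leaves one class of event outside the commitment, and the reporting filter applies under both. Two staff members could classify the same event differently, which makes counts by condition unreliable.

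**3. What other sections capture.** Central blood pressure, arterial stiffness, resting heart rate, heart rate variability, cytokines, mood (POMS) and vigilance (PVT) are outcomes (Sections 6.2 and 17.1). PVT and the sleep and activity logs are daily. None of these is described as recording clinical events such as falls, near-accidents or fainting.

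**4. Scale.**
- Restricted nights: 30 × 4 = 120 for the planned completers; 36 × 4 = 144 for the recruitment ceiling in 12.2. Restarts under 6.2 could add to this.
- Chance of at least one cardiac event or injury in n maximal tests, taking the 6 in 10,000 as a per-test risk: 1 − (1 − 0.0006)^n.
  - n = 36 (the ceiling in 12.2): 1 − 0.9994^36 = 2.1%.
  - n = 72 (assumed; the number screened is not stated): 1 − 0.9994^72 = 4.2%.
- Only tests in non-qualifiers fall under the destruction rule. If 36 people are tested and all qualify, there are none. If 72 are tested and 36 qualify, the other 36 tests carry about 2.1%.

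**The case against.** The strongest reply is that Section 18.1 is more than one bullet. It also promises safety information at every visit, an evaluation of harms, review by the team and a route for escalation. Nothing there excludes anticipated harms, and 15.4 has incidents reported for a hazard the protocol does anticipate. Sleep-related events missing from Section 15 could themselves count as unanticipated and so be recorded. This stands: a reader might infer that expected harms would certainly go uncounted, and the text does not establish that. It shows only that their capture is not assured, because the terms that decide it are undefined.

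A reader might also infer that the trial could not describe the harm of restricted against normal sleep. That goes too far. Comparing physiological, mood and vigilance responses by condition and fitness group is the trial's stated purpose. The gap is confined to clinical events and symptoms.

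A third tempting step is to read the quartile limits as meaning that about half of those tested will be turned away. The documents do not support a figure. Volunteers are recruited partly through fitness centers (13.1), and training status must match as well, so the share could be lower or higher.

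The destruction rule does not mention adverse-event records, so applying it to them is an inference. But the rule says all data and makes no exception. Finally, the consent form was not available for this review, so nothing can be said about what participants are told of sleep-restriction risks.

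**Conclusion.** The point holds as a gap in the recording rules. Section 18.1 commits explicitly only to unanticipated, reported events; it leaves two key terms undefined; and Section 15 is out of step with Section 3 on sleep restriction. Anticipated clinical events and symptoms may therefore be missing from the record and could not be reliably compared between sleep conditions. Events in people who fail to qualify have no protection from destruction.

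The 2.1% to 4.2% range rests on the protocol's own rate for cardiac event or injury, on independent tests, and on an assumed upper number of tests. With the 120 to 144 nights it shows scale only, and the conclusion does not depend on it. No sample size, power figure or primary analysis is affected. The change should be made before enrolment, or as early as possible, because events not recorded at the time are hard to recover.

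**What to change.** - **18.1:** record all adverse events, anticipated or not, with onset date and sleep condition. Use one standard question at each existing visit, and state what the safety information consists of.
- **4.2:** replace the template prompt with adverse events by sleep condition.
- **15.1:** reconcile the list of foreseeable risks with Section 3 on sleep restriction.
- **6.2:** exempt adverse-event records and a de-identified screening count from the destruction rule.

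The question should be tied to the scheduled visits. The weekly check-ins in 22.1 are described only for adherence to a supplementation protocol that this trial does not have, so they cannot be relied on as a contact.

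The cost is protocol wording, one question per visit and slightly more data entry. The intervention, visit schedule and sample size do not change; the only added analysis is a tabulation of events by condition.

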19.0 Provisions to Protect the Privacy Interests of Subjects

19.1 Only the research team will have access to personal information. Furthermore, it will be coded to protect participant privacy.

19.2 The research team will be kind, gentle, and explain every step of the research protocol to the participant prior to conducting each test of the experiment. Together, these conversations and familiarizations, paired with a friendly demeanor, will promote the participants of the study feeling at ease.

19.3 The research team may only access personal information about participant's by going through the PI. The PI is the only person who has access to the password protected computer and key to the locked drawer. The password and key will not be given out, ensuring the bottleneck of information going through the CITI trained PI.

Further, the data collected via the WHOOP and Sway Medical app will be provided, by the participant, to the PI for analysis of the data needed for study participation.

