5.0 Investigational Test Articles or Products

5.1 Device Description:

The WHOOP band (Boston, MA) is a wrist-worn multi-sensory biometric and cardio-autonomic function monitor. The device primarily collects continuous heart rate data and determines various metrics of well-being and cardio-autonomic (e.g., sleep, heart rate variability, resting heart rate, respiration rate, and recovery) via use of proprietary algorithms established by the company.

5.2 Device Handling/Usage:

The WHOOP band will be worn on the participant's non-dominant wrist throughout the entirety of the project timeline (~1.5 months), excluding anytime that the device might become submerged in water for extended periods of time (e.g., swimming or bathing). In order to use the device, the participant will need to and be instructed on how to download and use the smartphone application that accompanies the device. Upon completion of the study, the participant will return the device, and all accompanying equipment (i.e., device charger) to the primary investigator.

The Bod Pod (Cosmed, Chicago, IL) will be used to assess the participant's body composition during the initial visit. In order to perform the test, the participant will sit within in the device for a short period of time (~2 minutes) while the device measures the amount of air that is displaced by the participant (i.e., amount of air in the device while empty minus the amount of air in the device with the participant in the device). The air displacement value will then be used to estimate body composition via an automated program as part of the Bod Pod software.

The metabolic cart (Parvomedics; Salt Lake City, UT). will used to assess oxygen consumption and carbon dioxide production (i.e., metabolic testing) during the $\text{VO}_{2\text{max}}$ protocol, described in detail below. In order to use the device, the participant will don a face mask with a Hans Rudolph valve attached to it. The mask and valve allow for the inhalation of room air (i.e., normal breathing) while measuring expired air, via the cart, to establish metabolic values. Further, the mask will be worn for the duration of the test (~8-12 minutes).

The SphygmoCor Xcel device (AtCor Medical, New South Wales, Australia) will be used to assess central hemodynamics (i.e., central blood pressure) and arterial stiffness following the protocols set forth in the attached operations manual. In short, the participant will lie in a supine position while wearing

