two cuffs, one on their right arm and one on their right upper thigh. The arm cuff will be used for central blood pressure measurement following standard blood pressure testing. The thigh cuff will be used to measure arterial stiffness via applanation tonometry, a process involving the use of a tonometer to palpate for the participant's carotid pulse and assessing the time difference between the carotid pulse and femoral pulse (measured with the thigh cuff) for each heartbeat, resulting in the estimation of pulse transit time, a proxy for arterial stiffness.

The treadmill (4Front; Woodway USA, Waukesha, WI) will be used during the VO_{2max} test following the protocol outlined in the *VO_{2max} Testing Protocol* below.

The heart rate monitor (H10; Polar, Kempele, Finland) will be used to assess the participants heart rate during the VO_{2max} test. The participant will wear the device on the surface of the skin, superficial to the xyphoid process of the sternum (i.e., middle of the chest).

The Sway Medical application (Tulsa, OK) will be used to assess cognitive performance via two short (~1 minute) tests, reaction time and impulse control. In order to use the application, the participant will need to and be instructed on how to download and use the application. In short, both tests begin with a blank screen. For the reaction time test, participants will be tasked with tapping the blank screen as quickly as possible once the screen changes colors. For the impulse control test, the blank screen will display either a check mark or an X. Participants will be tasked with tapping the blank screen as quickly as possible if the check mark is displayed and avoiding tapping the screen if the X is displayed.

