approximate time of day for each individual to account for diurnal patterns in the data collected. In total, the protocol will last approximately 5 weeks and consist of 5 visits.

Central Hemodynamic Assessment: Participants will be assessed for central arterial pulse wave form and cf-PWV following both sleep interventions with re-analysis occurring 3 days later to quantify the response to, and recovery from, the two sleep interventions between the two groups. The central hemodynamic (i.e., central blood pressure, augmentation index [absolute and relative to a heart rate of 75 beats per minute], mean arterial pressure, and pulse pressure) and arterial stiffness (i.e., cf-PWV) variables of interest will be collected and analyzed following methods identical to those utilized by Grosicki, et al. (34).

Health and Well-Being Assessment: Both metrics of sleep quality and cardio-autonomic function (i.e., resting heart rate, heart rate variability, and a proprietary, WHOOP-generated recovery score) will be collected via the WHOOP devices. The wearing of the device throughout the entirety of the project timeline will allow for the quantification of these measures in response to, and recovery from, the two sleep interventions, which will be compared between the two groups. Further, data from the devices will be analyzed following protocols set forth by Greenwalt, et al. (44). Using blood samples collected during the venipuncture protocols performed at the four data collection visits, sleep intervention response and recovery levels of circulating plasma concentrations of pro- (CRP, IL-6, IL-1 β , and TNF- α) and anti-inflammatory (IL-10) cytokines will be assessed using protocols similar to that outlined by Smith, et al. (45). Additionally, portions of the blood samples will undergo hematologic analysis to characterize shifts in the composition of immune cells through methods similar to those of Schluter et al. (46). Finally, POMS data will be used to evaluate intervention-associated shifts in psychological mood states between the two groups following the methodology of Shacham (47).

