7.4 N/A

8.0 Sharing of Results with Subjects

- 8.1 Individual subject results for anthropometric data will be provided upon the completion of the study protocol. The results will be shared exclusively with the individual via print or word of mouth.

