Analysis of Variance: Central hemodynamic and arterial stiffness variables will be interpreted using a mixed-model (i.e., within-between) repeated measures analysis of variance (RMANOVA) to identify interactions between multiple groups and conditions. Specifically, to test the hypothesis that individuals with higher CRF would demonstrate a blunted arterial stiffness response (i.e., maintained pulse transit times) to the acute partial sleep deprivation intervention, cf-PWV will be assessed following 4 consecutive nights of both normal sleep and restricted sleep and compared between the two groups. Likewise, all secondary variables will be assessed at pre-specified time points using a within-between interaction RMANOVA to test the hypotheses that individuals with higher CRF would demonstrate a blunted effect of partial sleep deprivation on markers of physical and cognitive performance (i.e., maintained RSI and PVT, respectively) as well as on markers of overall health (i.e., maintained cardio-autonomic function parameters, pro- and anti-inflammatory serum cytokine levels, and mood states).

In the case that sphericity is violated, a Greenhouse-Geisser correction will be performed. In the case of significance, a post hoc one-way ANOVA with Bonferroni tests will be used to identify significant differences. Effect sizes (ES) will be calculated by standardizing mean differences to the standard deviations (SD) of the placebo condition. Effect sizes will be qualified as follows: small $d = 0.2$, moderate $d = 0.5$, and large $d \geq 0.8$ (50).

17.2 The data will be kept secure through several routes. First, only the CITI certified research team will be allowed to be involved in the data collection process. Further, after acute bouts of data collection occur, all data will be collected together by the PI. If the data is physical, it will be kept in a locked drawer, behind a locked laboratory door. If the data is electronic, it will be kept on a password secured computer that only the PI may gain access. All human data will be coded, such that without the code it becomes unidentifiable.

17.3 Quality control of collected data will be ensured by controlling as many external variables as is reasonable. Further, biological measures (primary outcomes) will be measured in duplicate with the average of each measure used in the final assessment.

17.4 Describe how data or specimens will be handled study-wide:

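### Participants run the WHOOP and Sway apps and hand over the data themselves, and nothing limits or records whether they view their own Aim 2 and 3 outcomes during the sleep blocks

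*Combined protocol and SAP*

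**What the plan says.** **Who operates the apps.** Section 5.2 says of WHOOP that "the participant will need to and be instructed on how to download and use the smartphone application that accompanies the device", and of Sway that "the participant will need to and be instructed on how to download and use the application". The band is worn "throughout the entirety of the project timeline (~1.5 months), excluding anytime that the device might become submerged in water", so it covers both four-day blocks and the washout. Section 6.2 has the reaction-time task done daily throughout enrolment.

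**What the apps hold.** Section 5.2 lists the WHOOP metrics as "sleep, heart rate variability, resting heart rate, respiration rate, and recovery". Section 6.2 makes resting heart rate, heart rate variability and the recovery score study outcomes ("a proprietary, WHOOP-generated recovery score) will be collected via the WHOOP devices"), and these belong to Aim 2. Psychomotor vigilance belongs to Aim 3.

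**How the data reach the study.** Section 19.3: "the data collected via the WHOOP and Sway Medical app will be provided, by the participant, to the PI".

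**Neighbouring rules.** Section 17.2 says that "only the CITI certified research team will be allowed to be involved in the data collection process". Sections 7.1 and 17.4 reserve access to the data for the verified research team. Section 8.1 says "Individual subject results for anthropometric data will be provided upon the completion of the study protocol".

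No section hides the app displays, tells participants not to look at their scores, records whether they looked, or plans an analysis of it.

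**The concern.** Sleep condition cannot be masked, because participants follow prescribed bed and wake times. That leaves self-reported and effort-dependent outcomes open to expectation. A daily score for recovery, sleep or reaction time would be a further and partly avoidable influence.

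A participant who sees a poor score may rate mood lower on the POMS, try less hard on the jump or the reaction test, or cut back training although 6.2 asks for usual activity. The POMS is completed at the post-test visit, after the block, so scores could have been seen by then.

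The hypotheses under all three aims predict a blunted response in the fitter group, which is tested as a group-by-condition interaction. Trained participants have more training to adjust than sedentary ones, so feedback could act differently in the two groups and resemble that interaction. Randomising the order of conditions does not remove this, because fitness is not randomised.

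There is a second, separate issue. Under 6.2, WHOOP data and sleep logs are used to judge compliance, and deviation leads to a restart. Under 14.1 non-compliance leads to withdrawal, and 13.5 makes the gift card depend on complete participation. The person with an interest in appearing compliant therefore supplies the record.

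**Working it through.** **1. From the text to access.**
- The participant downloads and uses both apps (5.2).
- The participant provides the data from both to the PI (19.3).
- A person who runs an app and supplies its data has access to at least some of its content. That this includes daily scores is a reasonable inference, but no section describes the screens.
- Section 5.2 describes Sway as the cognitive test application, and 6.2 refers to a smartphone application for psychomotor vigilance. I take these to be the same tool, since no other is described.

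**2. Which outcomes are exposed.**

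| Outcome | Source | Exposure |
|---|---|---|
| cf-PWV, central pressures | SphygmoCor, laboratory | Not app-derived |
| POMS | Self-report at visit | Feedback may colour the answers |
| Reaction time | Participant's phone, daily | Effort-dependent; scores possibly visible |
| RSI | Laboratory jump test | Effort-dependent |
| Recovery score, HRV, resting heart rate | WHOOP | Possibly visible; may move if training changes |
| Adherence | WHOOP and daily sleep logs | Both come through the participant |

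**3. Illustrative size.** The documents give no figure for a feedback effect, so the shift is an assumption.

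Inputs:
- 30 participants (12.1), taken as 15 per fitness group. The equal split is an assumption.
- Two-sided alpha 0.05 (17.1).
- No true interaction.
- Shift d = 0.25 to 0.5, in SDs of the within-person restricted-minus-normal difference, larger in one group than in the other by that amount.

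With two conditions, the group-by-condition test is a two-sample t test on the within-person differences. It has 15 + 15 − 2 = 28 degrees of freedom and critical value 2.048. The noncentrality is d × √(n/2) = d × √7.5 = d × 2.739.

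| Differential shift d | Noncentrality | Rejection rate |
|---|---|---|
| 0 | 0 | 5.0% |
| 0.25 | 0.685 | 10.1% |
| 0.50 | 1.369 | 26.2% |

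The row d = 0 also covers feedback that shifts both groups equally: it cancels in the interaction test, and the error rate stays at 5%.

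**4. The neighbouring rules beside 19.3.**
- Section 17.2 confines data collection to the certified team, and 7.1 and 17.4 confine access to the verified team. Taken literally, neither fits a participant who runs the apps and delivers the data.
- The 17.2 sentence, however, is part of a list of security measures. A literal reading would also rule out the sleep, activity and nutrition logs that 6.2 requires of participants. The wording is loose rather than a rule that the design breaks.
- Section 8.1 promises anthropometric results on completion. It does not say that these are the only results a participant may see, so it is silent on app data.

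**The case against.** The strongest reply is that little here is established. The documents do not say what the apps show. Participants know their sleep condition anyway, so only the added effect of a score is at issue. The primary objective rests on laboratory measurements taken by staff. A false interaction needs feedback to act differently by fitness group, and nothing in the documents shows that it does. All of this stands, and it limits the point to a plausible, unquantified risk to secondary outcomes.

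Three stronger readings are tempting and are not supported.
- **A contradiction of 8.1 or 17.2.** Section 8.1 forbids nothing, and 17.2 is a security provision that cannot sensibly exclude participant-generated data.
- **Transcription error.** Section 19.3 does not say that values are copied by hand; export or shared access would fit the sentence equally well.
- **A much larger error rate.** An equal shift of 0.25 to 0.5 SD in all 30 participants would make the main effect of condition falsely significant in 26% to 75% of trials. The hypotheses concern the interaction, where such a shift cancels.

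On adherence, it may be said that the sleep logs give a second record. They do, but participants complete those too, so they are not an independent check.

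Finally, an instruction not to look cannot be enforced, and dropping those who looked would be a post-randomisation exclusion from groups of about 15. Both points are right. The first does not make the instruction worthless. The second means that such an exclusion should not be a main remedy.

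**Conclusion.** The concern holds in a limited form. The plan gives participants operation of both apps and the task of delivering the data, and it says nothing about viewing. Access to Aim 2 and 3 outcomes during the blocks is therefore probable, and part of the adherence record passes through the person it judges.

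The size of any bias is unknown. The 10% to 26% range for a nominal 5% interaction test rests on an assumed differential shift of 0.25 to 0.5 SD, 15 per group and no true effect. It shows sensitivity and is not an estimate. The risk adds to the existing lack of masking and falls mainly on POMS, reaction time, RSI and activity; cf-PWV does not come from either app.

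The change is worth making before data collection, because feedback already seen cannot be undone and unrecorded viewing cannot be described afterwards. The issue of who supplies the adherence data stands whatever the size of the feedback effect.

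**What to change.** 1. Revise 19.3 so that the research team exports the WHOOP and Sway data directly at each visit, through accounts under the study code or shared access where the vendor allows it. Participants wear, charge and sync the band and take the test.
2. In 5.2, instruct participants not to open sleep, recovery, heart rate variability or past-score screens from the start of the first block until Recovery 2, except as needed to sync or take the test.
3. At each post-test visit, after the POMS, ask whether scores were viewed. Report the answers descriptively by fitness group and sleep condition. Label any analysis that leaves out viewers as exploratory.
4. Align the wording of 17.2 and 17.4 (and the matching sentence in 7.1) with 19.3, stating that participants generate some data themselves. Add to 8.1 a sentence on app-visible results.

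**Cost.** Wording changes, a small account set-up burden and one question at each of two visits. No extra participants or equipment are needed. The instruction cannot be fully enforced, and direct export depends on vendor functions that the documents do not describe.
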